16.1.4.4. Multiple Imputation with NRI to Handle Missing Data Due to COVID-19 Pandemic

The COVID-19 pandemic introduces unexpected and unknown impact on the clinical study due to unforeseen intercurrent events. As a sensitivity analysis, missing endoscopy data will be handled using a hybrid approach combining NRI and multiple imputation, where subjects with missing endoscopy data due to COVID-19 pandemic will be imputed using multiple imputation method under a MAR assumption, as described in Section 16.1.4.1. Missing data for any other reason will be considered a nonresponse.

16.1.5. Supplementary Analysis of Primary Efficacy Variables

The primary model as described in Section 16.1.3 will be repeated using the mFAS (with data as observed) and Per Protocol Set as supplementary analyses in subjects with Baseline MMS 5 to 9.

Analysis with the primary model as described in Section 16.1.3 will be repeated for both primary endpoints using the FAS with Baseline MMS 4 to 9. The multiple imputations, tipping point analysis, mFAS and Per Protocol Set analyses will also be repeated with Baseline MMS 4 to 9.

16.2. Key Secondary Efficacy

Key secondary efficacy endpoints are defined in Section 16. In general, all the primary and supplementary analyses planned for the primary endpoints in Section 16.1.3 and Section 16.1.4.4 will be repeated for each key secondary efficacy endpoint (Table 3). Additionally, the sensitivity analyses planned for the primary endpoints in Section 16.1.4 will be repeated for key secondary endpoints of endoscopic improvements and symptomatic remission (Table 3). Multiplicity adjustments for the family of the key secondary endpoints are discussed in Section 8.4.

Table 3: Planned Analyses by Endpoint

Endpoint	Primary Analysis of Stratified CMH	Sensitivity Analyses of MI, Tipping Point Analysis, MI with CR, and NRI + MI	Supplementary Analyses in mFAS and Per Protocol Set
Primary endpoints	X ^a	X	X
Key secondary endpoints:			
Endoscopic improvement	X	X	X
Symptomatic remission	X	X (MI, Tipping Point Analysis, and MI with CR only) ^b	X
Corticosteroid-free clinical remission	X		X
Mucosal healing	X	X (MI, MI-CR, and NRI + MI only)	X
Sustained clinical remission	X		X

^a Inference from the primary analysis method on the primary endpoints will be the gatekeeper for testing in the families of key secondary endpoints as per Section 8.4.

^b The hybrid missing data handling approach of NRI + MI will not be applied to the symptomatic remission endpoint since COVID 19 pandemic is not expected to impact subject eDiary entries.

Analyses in the table will be repeated for subjects in the specified analysis population with Baseline MMS 4 to 9. CMH, Cochran-Mantel-Haenszel; CR, copy reference; mFAS, modified full analysis set; MI, multiple imputation; NRI, nonresponder imputation.

16.2.1. Key Secondary Efficacy Variables and Derivations

16.2.1.1. Endoscopic Improvement

For each of the 2 timepoints (Week 12 and Week 52):

The null hypothesis is that the proportion of subjects achieving endoscopic improvement is the same between etrasimod and placebo.

The alternative hypothesis is that the proportion of subjects achieving endoscopic improvement is different between etrasimod and placebo.

16.2.1.2. Symptomatic Remission

For each of the 2 timepoints (Week 12 and Week 52):

The null hypothesis is that the proportion of subjects achieving symptomatic remission is the same between etrasimod and placebo.

The alternative hypothesis is that the proportion of subjects achieving symptomatic remission is different between etrasimod and placebo.

16.2.1.3. Corticosteroid-Free Clinical Remission and Sustained Clinical Remission

For corticosteroid-free clinical remission:

The null hypothesis is that the proportion of subjects achieving corticosteroid-free clinical remission at Week 52 is the same between etrasimod and placebo.

The alternative hypothesis is that the proportion of subjects achieving corticosteroid-free clinical remission at Week 52 is different between etrasimod and placebo.

For sustained clinical remission:

The null hypothesis is that the proportion of subjects achieving sustained clinical remission (ie, at both Week 12 and Week 52) is the same between etrasimod and placebo.

The alternative hypothesis is that the proportion of subjects achieving sustained clinical remission (ie, at both Week 12 and Week 52) is different between etrasimod and placebo.

16.2.1.4. Mucosal Healing

For each of the 2 timepoints (Week 12 and Week 52):

The null hypothesis is that the proportion of subjects with mucosal healing is the same between etrasimod and placebo.

The alternative hypothesis is that the proportion of subjects with mucosal healing is different between etrasimod and placebo.

16.2.2. Missing Data Methods for Key Secondary Efficacy Variables

The same missing data methods used for the primary endpoints described in Section 16.1.2 will be used for the key secondary endpoints.

16.2.3. Primary Analysis of Key Secondary Efficacy Variables

The primary analysis of these key secondary efficacy endpoints will be performed for the FAS with Baseline MMS 5 to 9. For all key secondary endpoints, the model described in Section 16.1.3 will be used.

16.2.4. Sensitivity Analysis of Key Secondary Efficacy Variables

For the key secondary endpoints of endoscopic improvement, symptomatic remission, and mucosal healing, the sensitivity analyses described in Section 16.1.4 will be used.

16.2.5. Supplementary Analysis of Key Secondary Efficacy Variables

For all key secondary endpoints, the primary model as described in Section 16.1.3 will be repeated using the mFAS (with data as observed) and Per Protocol Set as supplementary analyses with Baseline MMS 5 to 9.

For the key secondary endpoints, analyses listed in Table 3 will be repeated in subjects with Baseline MMS 4 to 9.

16.3. Other Secondary Efficacy

Other secondary efficacy endpoints are defined in Section 16.

16.3.1. Other Secondary Efficacy Variables

The other secondary endpoints are:

- The proportion of subjects who had not received corticosteroids for ≥ 4 weeks and achieved clinical remission at Week 52 among subjects receiving corticosteroids at baseline
- The proportion of subjects achieving clinical response at Week 52
- The proportion of subjects achieving clinical response at Week 12
- The proportion of subjects achieving clinical response at both Weeks 12 and 52
- The proportion of subjects with mucosal healing at both Weeks 12 and 52
- The proportion of subjects achieving endoscopic normalization at Week 52
- The proportion of subjects achieving endoscopic normalization at Week 12
- The proportion of subjects achieving endoscopic normalization at both Weeks 12 and 52
- The proportion of subjects achieving symptomatic remission at Weeks 2, 4, 8, 16, 20, 24, 32, 40, and 48
- The proportion of subjects achieving complete symptomatic remission at each study visit (Weeks 2, 4, 8, 12, 16, 20, 24, 32, 40, 48, and 52)
- The proportion of subjects achieving noninvasive clinical response at each study visit (Weeks 2, 4, 8, 12, 16, 20, 24, 32, 40, 48, and 52)
- The proportion of subjects achieving symptomatic response at each study visit (Weeks 2, 4, 8, 12, 16, 20, 24, 32, 40, 48, and 52)
- The proportion of subjects achieving clinical remission at Week 52 among subjects in clinical response at Week 12

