10.12. Testing Strategy

10.12.1. Efficacy Analysis

The primary analysis of the proportion-based efficacy endpoints will be carried out using the Cochran-Mantel-Haenszel (CMH) method, stratified by (a) naïve to biologic or JAK inhibitor therapy at study entry (yes or no), (b) baseline corticosteroid use (yes or no), and (c) baseline disease activity (MMS: 4 to 6 or 7 to 9). Results will be expressed as the number of subjects in remission, remission percentages, difference in remission percentages, odds ratio, and associated 95% confidence intervals (CIs) and p-values.

There are multiple null hypotheses for the comparison of etrasimod and placebo in the primary and key secondary endpoints. The family-wise type-I error rate will be controlled at a fixed α level at 0.025 (1-sided) using the following testing procedure. First, the whole α will be spent on testing both of the primary endpoints. This study will be considered as an overall success only if both of the primary null hypotheses are rejected, each at the α level (as coprimary hypotheses). This study will be considered as a partial success if only one of the two primary null hypotheses are rejected at $\alpha/2$ if the other has $p > \alpha$.

Only if both of the primary null hypotheses are rejected, each at the α level, can testing proceed for the 8 key secondary endpoints. The method for such testing will be specified in the SAP, and it will control for the multiplicity of the 8 key secondary endpoints. Any key secondary endpoint that fails to be significant at the α level by this method to control multiplicity will be considered exploratory and thereby would only have nominal p-values. All other endpoints will be evaluated at α level of significance and reported with nominal p-values, without multiplicity adjustment.

Full details of the efficacy analysis will be documented prior to database lock in the SAP.

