2.5. Estimands

The primary and key secondary efficacy estimands to support regulatory decisions are described in Table 1. The analyses will be performed on the Full Analysis Set (FAS) as defined in Section 5.3. Other secondary efficacy variables (specified in Section 16.3.1) will have the population, intercurrent event handling strategy and population-level summary measure similar to the primary estimand. Supplementary analyses for the primary and the key secondary estimands will be performed on the modified Full Analysis Set (mFAS) and the Per Protocol populations, respectively (ICH 2019). Intercurrent events include: 1) initiate a rescue medication for UC, 2) have an increase in dose over Baseline levels in their existing UC medication, or 3) have a rescue non-drug treatment (eg, colectomy, ileostomy, or sigmoidectomy) before the

efficacy assessment. Refer to [APPENDIX 7](#) for the definition of rescue therapies (medication and medical procedures).

Table 1: List of Primary and Key Secondary Estimands

Estimand	Definition	Attribute			
		Population	Variable/Endpoint	Intercurrent Event Handling Strategy	Population-Level Summary Measure
Primary Estimand 1	Efficacy of etrasimod on clinical remission at Week 12	Randomized subjects who receive at least 1 dose of study treatment and with Baseline MMS 5 to 9	The proportion of subjects with SF = 0 (or = 1 with a ≥ 1 -point decrease from Baseline), RB = 0, and ES ≤ 1 (excluding friability) at Week 12	Subjects with any of the 3 intercurrent events ^a before the efficacy assessment will be treated as nonresponders.	Difference between etrasimod and placebo in the endpoint at Week 12
Primary Estimand 2	Efficacy of etrasimod on clinical remission at Week 52	Randomized subjects who receive at least 1 dose of study treatment and with Baseline MMS 5 to 9	The proportion of subjects with SF = 0 (or = 1 with a ≥ 1 -point decrease from Baseline), RB = 0, and ES ≤ 1 (excluding friability) at Week 52	Subjects with any of the 3 intercurrent events ^a before the efficacy assessment will be treated as nonresponders.	Difference between etrasimod and placebo in the endpoint at Week 52

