6.5. Statistical Tests

The default significance level will be 0.05; confidence intervals (CIs) will be 95%, and all tests will be 2-sided, unless otherwise specified in the description of the analyses.

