16. EFFICACY OUTCOMES

Unless otherwise stated, the primary efficacy analyses will be based on subject stratum used at the time of randomization for the FAS with Baseline MMS 5 to 9. Primary and key secondary efficacy analyses will be repeated for all subjects in FAS with Baseline MMS 4 to 9 as a supplementary analysis. The following definitions will be used to assess efficacy outcomes:

- Clinical response: A ≥ 2 -point and $\geq 30\%$ decrease from Baseline in MMS, and a ≥ 1 -point decrease from Baseline in RB subscore or an absolute RB subscore ≤ 1
- Clinical remission: SF subscore = 0 (or = 1 with a ≥ 1 -point decrease from Baseline), RB subscore = 0, and ES ≤ 1 (excluding friability)
- Endoscopic improvement: ES of ≤ 1 (excluding friability)
- Endoscopic normalization: ES = 0
- Mucosal healing: ES of ≤ 1 (excluding friability) with histologic remission measured by a Geboes Index score < 2.0
- Symptomatic remission: SF subscore = 0 (or = 1 with a ≥ 1 -point decrease from Baseline) and RB subscore = 0
- Complete symptomatic remission: SF subscore = 0 and RB subscore of 0
- Symptomatic response: Decrease from Baseline $\geq 30\%$ in composite RB and SF subscores
- Noninvasive clinical response: A $\geq 30\%$ decrease from Baseline in composite RB and SF, and a ≥ 1 -point decrease from Baseline in RB subscore or an absolute RB subscore ≤ 1
- Histologic improvement: Geboes Index score ≤ 3.1
- Histologic remission: Geboes Index score < 2.0
- Histologic improvement using Roberts Histopathology Index (RHI): $\geq 50\%$ reduction from Baseline in RHI or RHI ≤ 3
- Histologic remission using RHI: RHI ≤ 3 , with scores of 0 (zero) for both Geboes Grade 2B (lamina propria neutrophils) and Grade 3 (neutrophils in epithelium)
- Histologic improvement using Nancy Histologic Index (NHI): ≥ 1 point reduction from Baseline NHI
- Histologic remission using NHI: ≤ 1

- Clinical remission using total Mayo Clinic score: total Mayo Clinic score of ≤ 2 points with no individual subscore of > 1 point
- Clinical response using total Mayo Clinic score: $A \geq 3$ -point and $\geq 30\%$ decrease from Baseline in total Mayo Clinic score, and a ≥ 1 -point decrease from Baseline in RB subscore or an absolute RB subscore ≤ 1
- Corticosteroid-free clinical remission: Clinical remission at Week 52 and who had not been receiving corticosteroids for ≥ 12 weeks prior to Week 52
- Sustained clinical remission: Clinical remission at both Week 12 and Week 52
- Loss of response:

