16.1.3. Primary Analysis of Primary Efficacy Variables

The following hypotheses (H_{01} and H_{02}) for the coprimary endpoints will be tested:

H_{01} : The proportion of subjects achieving clinical remission at Week 12 is the same between etrasimod and placebo.

H_{11} : The proportion of subjects achieving clinical remission at Week 12 is different between etrasimod and placebo.

H_{02} : The proportion of subjects achieving clinical remission at Week 52 is the same between etrasimod and placebo.

H_{12} : The proportion of subjects achieving clinical remission at Week 52 is different between etrasimod and placebo.

Both hypotheses will be tested at the 2-sided α level, 0.05.

The primary efficacy analysis will be performed for the FAS with Baseline MMS 5 to 9. The Cochran-Mantel-Haenszel (CMH) test will be used, stratified by naïve to biologic or JAK inhibitor therapy at study entry (Yes or No), Baseline corticosteroid use (Yes or No), and Baseline disease activity (MMS: 4 to 6 or 7 to 9). Reported randomization stratum will be used in the model. Results will be expressed as the number and percentage of subjects in remission, difference in remission percentages and 95% CI and p-value, odds ratio and 95% CI. If there are no responders in both treatment groups in any stratum, the difference in remission percentages and associated inferences can still be made. However, the odds ratio and its CI may be calculated from the unstratified CMH.

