16.3.3. Analysis of Other Secondary Efficacy Variables

The analysis of other secondary efficacy endpoints will be performed for the FAS with Baseline MMS 5 to 9. The primary analysis method planned for the primary endpoints in Section 16.1.3 will be repeated for each other secondary efficacy endpoint. No multiplicity adjustment will be made.

will be analyzed using the stratified CMH model described in Section 16.1.3 for the FAS with Baseline MMS 5 to 9.

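### Week 52 remission among Week 12 responders is tested between arms although the denominator is a post-randomisation outcome, so the difference, CI and p-value are not a randomised treatment comparison

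*SAP*

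**What the plan says.** SAP 16.3.1 ends its list of other secondary endpoints with "The proportion of subjects achieving clinical remission at Week 52 among subjects in clinical response at Week 12". Section 16 defines clinical response by a "decrease from Baseline in MMS" of a set size plus a rectal bleeding condition, so at Week 12 it is known only after 12 weeks on randomised treatment. Clinical response at Week 12 is itself an efficacy endpoint in the same list.

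SAP 16.3.3 makes no exception for this endpoint: "The primary analysis method planned for the primary endpoints in Section 16.1.3 will be repeated for each other secondary efficacy endpoint". Under 16.1.3 that method is a CMH test stratified by biologic/JAK-naive status, baseline corticosteroid use and baseline MMS group, reporting "difference in remission percentages and 95% CI and p-value, odds ratio and 95% CI". SAP 6.5 sets the level: "The default significance level will be 0.05; confidence intervals (CIs) will be 95%, and all tests will be 2-sided".

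On status, 16.3.3 says "No multiplicity adjustment will be made", and protocol 10.12.1 has all endpoints outside the primary and key secondary families "reported with nominal p-values, without multiplicity adjustment". On population, SAP 2.5 says the other secondary variables "will have the population, intercurrent event handling strategy and population-level summary measure similar to the primary estimand", and 16.3.3 names the FAS with Baseline MMS 5 to 9.

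Nothing in the supplied text marks this endpoint as descriptive, defines an estimand for Week 12 responders, or deals with the selection.

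**The concern.** Subjects are randomised once, 2:1, and those who stay in after Week 12 keep their assigned treatment (SAP 3.1). Randomisation makes the arms comparable at baseline. It does not make etrasimod responders comparable with placebo responders if the drug affects who responds. Etrasimod responders may then be a mixture of subjects who would have responded anyway and subjects who responded because of the drug, while placebo responders are only the first kind. The CMH factors are baseline variables and do not balance that mixture.

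Two features of the SAP add to the problem. A responder-only denominator fits neither the population in 2.5 nor the one in 16.3.3. And 16.3.2 treats missing data as nonresponse: elsewhere this counts a subject as a failure, but here, on a plain reading, a subject with missing Week 12 status leaves the denominator.

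At stake is interpretation. The output invites the reading that it shows how well etrasimod maintains benefit in responders, and a p-value gives that reading weight the design cannot support.

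**Working it through.** **The plan's own figure.** The documents state no power or sample size for this endpoint. The nearest figure is 93.4% power for Week 52 remission (SAP 7: 23.5% vs 10.0%, 280 vs 140, one-sided 0.025, Fisher's exact). Exact enumeration gives 92.8% and a normal approximation 93.9%, so the rates and allocation are read as intended.

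**Inputs.** From SAP 7: 280 and 140 subjects; Week 52 remission 23.5% and 10.0%. Assumed, because the documents do not give them: Week 12 clinical response r_E (etrasimod) and r_P (placebo), and how Week 12 response relates to Week 52 remission.

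**Step 1: where the bias comes from.** Suppose every placebo responder would also respond on etrasimod, and that treatment changes no subject's Week 52 remission probability. Let q_A be that probability in subjects who respond on either arm, and q_I in those who respond only because of etrasimod.

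- Placebo conditional rate = q_A
- Etrasimod conditional rate = [r_P q_A + (r_E - r_P) q_I] / r_E
- Difference = [(r_E - r_P) / r_E] x (q_I - q_A)

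The difference is zero if r_E = r_P or q_I = q_A. Otherwise, when etrasimod raises response, it takes the sign of q_I - q_A. With r_E = 55% and r_P = 35%, so (r_E - r_P)/r_E = 0.20/0.55:

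- q_A = 30%, q_I = 10%: 0.20/0.55 x (-20) = -7.3 points (22.7% vs 30.0%)
- q_A = q_I = 25%: 0
- q_A = 20%, q_I = 35%: 0.20/0.55 x (+15) = +5.5 points (25.5% vs 20.0%)

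**Step 2: size under a latent-correlation model.** Give each subject correlated normal Week 12 and Week 52 scores with correlation rho, and cut them at the assumed rates. The conditional rate in an arm is Phi2(z_r, z_q; rho) / r, where z_r and z_q are the normal quantiles of r and q. Week 52 remission is q = 10% in both arms and r_P = 35%. Entries are etrasimod vs placebo conditional percentages; differences are taken before rounding.

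| r_E | rho 0.3 | rho 0.5 | rho 0.7 |
|---|---|---|---|
| 45% | 14.70 vs 15.95: -1.2 | 17.79 vs 20.27: -2.5 | 20.58 vs 24.70: -4.1 |
| 50% | 14.16 vs 15.95: -1.8 | 16.76 vs 20.27: -3.5 | 18.94 vs 24.70: -5.8 |
| 60% | 13.19 vs 15.95: -2.8 | 14.97 vs 20.27: -5.3 | 16.25 vs 24.70: -8.5 |

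At rho = 0 every difference is zero. With rho positive and equal Week 52 rates, this model makes the arm with more responders look worse, so the negative sign comes from the model and is not a finding.

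**Step 3: effect on the test.** The Step 1 model was simulated with 280 vs 140 subjects, 200,000 trials per scenario, and an unstratified two-sided z test at 0.05 standing in for CMH.

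- In the -7.3 point case, with 2% Week 52 remission in never-responders, the conditional test rejects 18.8% of the time, 18.7% in the direction of harm. Week 52 remission over all randomised subjects is 13.4% in both arms and its test rejects 4.9%.
- Across the scenarios tried, conditional rejection is about 5% when there is no Week 12 effect or prognosis is equal; 6.6% to 50.3% when the extra responders do worse (-2.2 to -16.4 points); and 6.8% to 15.2% when they do better (+3.3 to +8.2 points). The all-randomised test stays at 4.8% to 5.0%.

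**Step 4: with a real Week 52 effect.** Take 23.5% vs 10.0% and assume every Week 52 remitter was a Week 12 responder. The conditional difference is 0.235/r_E - 0.10/r_P.

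- r_E = 45%, r_P = 35%: 52.2% - 28.6% = +23.7 points
- r_E = 75%, r_P = 25%: 31.3% - 40.0% = -8.7 points

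The sign reverses once r_E/r_P exceeds 0.235/0.10 = 2.35. The same Week 52 benefit can thus give a large positive or a negative conditional difference, depending on Week 12 response.

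**The case against.** The strongest reply is that little hangs on this endpoint. It is outside the gatekeeping, its p-value is nominal, and all-subject durability endpoints are already planned: sustained clinical remission as a key secondary, and clinical response, mucosal healing and endoscopic normalization at both Weeks 12 and 52. That stands, and it limits the point to labelling one output.

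A second reply is that the illustration is chosen to look bad. At the planning rates and 60% vs 35% response, the Step 2 model gives conditional differences of about 13.4, 12.8 and 11.9 points, close to the unconditional 13.5. The Step 2 table needs no Week 52 effect, and the coprimary result would then stand beside it. This is fair as a limit on the illustration. It does not make the comparison a randomised one, and Step 4 shows that the planning rates give no general protection.

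A reader might infer that the bias must run against etrasimod, because drug-induced responders are the harder cases. The documents do not support that: nothing in them gives the Week 52 prognosis of such subjects, and Step 1 gives either sign.

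A further reply is that an all-subject composite does not isolate maintenance either. That is right. Under the 10% vs 10% assumption at 60% vs 35% response, the joint rates are 7.91% vs 5.58%, 8.98% vs 7.09% and 9.75% vs 8.64%, so the composite favours etrasimod by 2.3, 1.9 and 1.1 points through the Week 12 effect alone. It is a valid randomised comparison, but of a different quantity.

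The supplied protocol text breaks off within its list of other secondary endpoints, so nothing is inferred from the protocol about this one.

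**Conclusion.** The point holds as a design matter that can be read directly from SAP 16, 16.1.3, 16.3.1 and 16.3.3: a between-arm CMH analysis is applied to a subset chosen by a post-randomisation outcome. The resulting difference, CI, odds ratio and p-value do not estimate a treatment effect protected by randomisation.

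Bias needs two conditions together: an effect of etrasimod on Week 12 response, and a different Week 52 prognosis in drug-induced responders. The documents establish neither its size nor its sign. The -1.2 to -8.5 point range rests on assumed response of 45% to 60% vs 35%, equal 10% Week 52 remission and latent correlation 0.3 to 0.7. The rejection rates rest on the assumed prognoses, the full 280/140 rather than the MMS 5 to 9 subset (whose size is not given), and an unstratified test.

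A reader might also infer that the trial's efficacy conclusions are in doubt. They are not: no primary or key secondary conclusion depends on this endpoint. Nor does the problem extend to the other restricted endpoint in 16.3.1, which selects on corticosteroid use at baseline.

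**What to change.** In SAP 16.3.3, exempt this one endpoint from the between-arm CMH analysis. Report the percentage of Week 12 responders in remission at Week 52 by arm, with numerator and denominator, as a descriptive figure without a difference, CI, odds ratio or p-value.

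If a comparison is wanted, add to 16.3.1 the composite of clinical response at Week 12 and clinical remission at Week 52, with all subjects in the FAS with Baseline MMS 5 to 9 in the denominator and the same CMH method. This follows the form the SAP already uses for response at both timepoints. Label it as a composite that also reflects the Week 12 effect, not as a pure maintenance effect.

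The cost is wording in two SAP sections, with the same data and essentially the same program. The downside is that the conditional percentage loses its nominal p-value.
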